**Multicenter double-blind placebo-controlled parallel group
randomized clinical study of efficacy and safety of Raphamin in the
treatment of acute respiratory viral infection in children aged 12-18
years**

Phase III

Sponsor	ООО «NPF «MATERIA MEDICA HOLDING»
Protocol number	MMH-407-003
Version date:	November 10, 2020
ClinicalTrials.gov Id:	NCT04918771

Protocol Summary

This document represents the protocol summary for the study on human patients. The study will be carried out in accordance with ICH GCP, Helsinki Declaration of World Medical Association, Rules of good clinical practice, approved by order of the Ministry of Health of the Russian Federation dated April 1, 2016 N 200n, , relevant requirements of the regulatory authorities as well as the study procedures.

Title of Study

Multicenter double-blind placebo-controlled parallel group randomized clinical study of efficacy and safety of Raphamin in the treatment of acute respiratory viral infection in children aged 12-18 years.

Phase: III

Sponsor: OOO «NPF "MATERIA MEDICA HOLDING», Moscow, Russia

Protocol No. MMH-407-003

Objective of the study

- To evaluate the efficacy and safety of Raphamin in the treatment of acute respiratory viral infection (ARVI) in children aged 12-18 years.

Endpoints

Primary endpoint

1. Time to resolution of ARVI^{1,2} symptoms (PCR-confirmed).

Secondary endpoints

1. ARVI severity (clinically diagnosed and/or PCR-confirmed; based on the area under the curve (AUC) results for the total severity index³ from days 1 to 6 of observation).
2. Percentage of patients with resolution of ARVI symptoms (clinically diagnosed and/or PCR-confirmed).
3. Time until resolution of ARVI symptoms, (clinically diagnosed and/or PCR-confirmed).
4. Percentage of patients with resolution of ARVI symptoms (PCR-confirmed).

¹Time from symptom onset at visit 1 until resolution of the disease symptoms.

Resolution of ARVI symptoms will be defined if temperature is $\leq 37.3^{\circ}\text{C}$ within 24 hours (without further increase during observation period) + lack/presence of systemic ARVI symptoms ≤ 2 .

² Based on a patient diary.

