³**Total severity index** will be calculated from the rating scores obtained for each of the symptoms of upper respiratory infection (body temperature, general/non-specific flu-like symptoms, and nasal/throat and chest symptoms) with subsequent statistical processing of data by specialists of OOO "NPF "MATERIA MEDICA HOLDING". To determine total score, absolute values of body temperature measured in Celsius degrees will be converted into relative units (or points) based on the following classification: $\leq 37.3^{\circ}\text{C}=0$; $37.4-38.0^{\circ}\text{C}=1$; $38.1-39.0^{\circ}\text{C}=2$; $\geq 39.1^{\circ}\text{C}=3$.

5. Number of antipyretics taken according to indications on days 1-3 of treatment⁴.
6. Percentage of patients with worsening of the disease (development of complications requiring antibiotics or hospitalization) on days 4-14 from the onset of observation.

Safety assessment

1. Adverse events (AEs) during the therapy, AEs severity and relation to the study drug, and AEs outcomes.
2. Changes in vital signs during the treatment.
3. Percentage of patients with clinically relevant laboratory abnormalities.

Study design

Study design: multicenter, double blind, placebo-controlled, parallel group randomized clinical trial.

The study will enroll outpatients of either gender aged 12-18 years with clinical manifestations of ARVI within the first days after onset of the disease. The patients will be recruited during seasonal ARVI morbidity. Collection of history, thermometry, objective examination, laboratory tests, recording concomitant therapy will be made after parent/adoptive parent signing information sheet and informed consent form for the child participation in the clinical study, for children ≥ 14 years old after signing patient information sheet and informed consent form for children ≥ 14 years old to participate in the clinical study. The severity of ARVI symptoms will be evaluated according to 4-point scale "Symptom Severity Score" (0 = no symptom, 1 = mild symptom, 2 = moderate symptom, and 3 = severe symptom).

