The nasopharyngeal swabs for PCR diagnosis and verification of respiratory viruses will be performed prior to therapy to confirm the viral etiology of ARVI. To exclude the infection caused by the new coronavirus COVID-19 (Coronavirus disease 2019), a rapid test for SARS-CoV-2 antigen will be made. In case of a positive SARS-CoV-2 test, the physician will act in accordance with the current version of the Ministry of Health of the Russian Federation Temporary methodological recommendations "Prevention, diagnosis, and therapy of new coronavirus infection (COVID-19)".

If a patient meets all inclusion criteria and does not have any exclusion criteria, at Visit 1 (Day 1), he/she will be randomized into one of two groups: patients of group 1 will take Raphamin according to the dosage regimen for 5 days; patients of group 2 will take Placebo using Raphamin 5-day regimen.

The study will use an electronic patient diary (EPD) for recording morning and evening axillary

⁴ Based on a patient diary.

body temperature (using a classic mercury-free thermometer) and disease symptoms (Symptom Severity Score). Besides, antipyretic dosing (if applicable) and any worsening in a patient's condition (if applicable, for safety evaluation/AE registration) will also be recorded in a patient diary. The investigator will provide instructions on filling the diary. At Visit 1 the parent/adoptive parent together with an investigator will record ARVI symptom severity and body temperature in the diary.

Patients will be observed for 14 days (screening, randomization - up to 1 day, treatment period – 5 days, follow-up – up to 2 days; deferred "phone visit" – day 14).

During the treatment and follow-up period the patients/physicians will pay 3 visits and the fourth "phone visit" will be scheduled additionally: 1) visits by physician/patient - on Days 1, 5, and 7 (Visits 1, 2, and 3) - in a study center or at home; 2) "phone visit" (Visit 4) - on Day 14.

At Visits 2 and 3, the investigator will perform an physical examination, document changes in the symptoms and concomitant medications, and check patient diaries. At Visit 3 laboratory tests will be performed and compliance will be checked.

"Phone visit" will be performed to interview parents/adoptive parents about the patient's condition, presence/absence of secondary bacterial/viral complications, and use of antibiotics.

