During the study, symptomatic therapy and therapy for their comorbidities are allowed with the exception of the drugs indicated in the section "Prohibited Concomitant Treatment".

Inclusion and exclusion criteria

Inclusion criteria

1. Patients of either gender aged 12 to 18 years.
2. Diagnosis of ARVI based on medical examination: axillary temperature $\geq 37.8^{\circ}\text{C}$ at examination + non-specific flu-like symptoms score ≥ 4 points, nasal/throat/chest symptom score ≥ 2 points.
3. The first 24 hours after ARVI onset.
4. Contraceptive measures by sexually active adolescents of both genders during the study.
5. Patient information sheet (informed consent form) signed by one parent/adoptive parent of the patient and there is also a signed patient information sheet (informed consent form) for children aged 14 and over.

Exclusion criteria

1. Clinical symptoms of severe influenza/ARVI requiring hospitalization.
2. Positive SARS-CoV-2 (COVID-19/Coronavirusdisease2019) antigen test.

3. Suspected pneumonia, bacterial infection (including otitis media, sinusitis, urinary tract infection, meningitis, sepsis, etc.) requiring administration of antibiotics from the first day of illness.
4. Suspected initial manifestations of diseases with symptoms similar to ARVI at onset (other infectious diseases, flu-like syndrome at the onset of systemic connective tissue diseases, and other pathology).
5. Patients requiring antiviral medication prohibited within the study.
6. Medical history of primary and secondary immunodeficiency.
7. Medical history/suspicion of oncology of any localization (except for benign neoplasms).
8. Exacerbation or decompensation of chronic diseases (diabetes mellitus, children cerebral paralysis, cystic fibrosis, primary ciliary dyskinesia, bronchopulmonary dysplasia, respiratory and ENT congenital defects, etc.) affecting a patient's ability to participate in the clinical trial.
9. Malabsorption syndrome, including congenital or acquired lactase or other disaccharidase deficiency, galactosemia.
10. Allergy/ hypersensitivity to any component of the study drugs used in the treatment.
11. Pregnancy. Breast-feeding.
12. Use of medications specified in the section "Prohibited Concomitant Therapy" within two weeks prior to inclusion in the study.
13. Patients whose parents/adopters, from the investigator's point of view, will not comply with the observation requirements during the study or follow the procedure for taking the study drugs.

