⁶ If, considering the lack of some data in primary endpoint variable, the fact of reaching the primary endpoint by the patient can still be determined, the patient will be eligible for PP analysis (e.g. the diary lacks some records but the time of recovery can still be determined).

⁷ No more than 10% patients who signed PIS and ICF are expected to be screening failures for various reasons.

1.5 the ratio between the sample sizes of the study drug and placebo groups is 1:1 (1 study drug patient - 1 placebo patient);

1.6 statistical hypotheses: null and alternative hypotheses about the superiority of the study drug over placebo using the applied dosing regimen:

primary endpoint:

$$H_0: M_1 - M_2 = 0$$

$$H_a: M_1 - M_2 \neq 0$$

where : M_1 – average time to resolution of the symptoms in the Raphamin group,

M_2 – average time to resolution of the symptoms in the Placebo group.

Sample analysis will be performed according to the following formulas:

$$n_1 = kn_2$$

$$n_2 = \frac{(z_{\alpha/2} + z_{\beta})^2 * (1 + 1/k)\sigma^2}{\varepsilon^2}$$

where n_2 , n_1 is sample size in study drug and placebo groups, respectively;

$\varepsilon = M_1 - M_2$ is the time difference between Raphamin and Placebo groups;

k – coefficient of Raphamin/Placebo sample ratio ($k=1$);

σ - standard deviation;

$z_{\alpha/2}$ – tabular value of two-sided z-test for α ;

z_{β} – tabular value of one-sided z-test for β ;

1.7 Full sample size is determined using the formula:

$$N = N_{pp} / (1 - R_w),$$

where N – the final sample size;

N_{pp} – result of calculation in cl. 1.6, i.e. scheduled number of the patients completing the study per protocol;

R_w – withdrawal rate.

2. Assumptions on expected effects of the clinical study: The differences in duration of the disease between the groups is expected to be less than 1 day, with standard deviation in the groups of no more than 2.5^8 days.

Therefore, the number needed to compare study drug and placebo will be **200** patients for both groups. Given potential withdrawal of at least 50%⁹ patients ($R_w = 0.5$) during the study for

⁸Upper limit of confidence interval of standard deviation of the time to resolution of the symptoms for placebo group based on the results of study MMH-ER-009 "International multicenter double-blind placebo-controlled randomized parallel-group clinical study of efficacy and safety of Ergoferon in the treatment of acute respiratory viral infections in children".

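### Does the missing unit in the symptom part of the primary resolution rule leave the endpoint in need of change?

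*Combined protocol and SAP*

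**What the plan says.** The document describes itself in its opening lines: "This document represents the protocol summary for the study on human patients".

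Footnote 1 to the Endpoints section defines resolution by two parts. The temperature must be at most 37.3 °C over 24 hours with no later rise, and the symptom part reads "lack/presence of systemic ARVI symptoms ≤ 2". Footnote 2 takes the data from the patient diary. The rule dates the primary endpoint and is the natural definition for secondary endpoints 2 to 4, which concern the same resolution.

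Three other places bear on the symptom part:

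- The Study design section gives the scale for each symptom: "0 = no symptom, 1 = mild symptom, 2 = moderate symptom, and 3 = severe symptom".
- Footnote 3 names the components of the total severity index: "body temperature, general/non-specific flu-like symptoms, and nasal/throat and chest symptoms".
- Inclusion criterion 2 sets entry thresholds with a unit: "non-specific flu-like symptoms score ≥ 4 points, nasal/throat/chest symptom score ≥ 2 points".

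On temperature, the Study design section has the electronic diary used for "recording morning and evening axillary" temperature, along with symptom scores. The section on indications for antipyretics adds a temperature to be recorded before an antipyretic is given.

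**The concern.** The entry criterion counts in points, while the resolution rule gives a bare 2. Three units can be put behind it: at most two symptoms present, at most two points in total, or no symptom graded above 2. The word *systemic* describes symptoms only in this rule, and no list of items is given. It is also not said whether the readings before an antipyretic count towards the temperature part.

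If analysts had to guess, the date of resolution could differ between readings for the same patient. That would affect the primary endpoint, the secondary endpoints built on resolution, and possibly who stays in the per protocol set. If the unit were chosen after unblinding, the choice could raise the chance of a false positive result.

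**Working it through.** **Do the readings differ?** Each present symptom scores 1, 2 or 3. With one or two symptoms present there are 3 single scores and 6 unordered pairs, 3 + 6 = 9 patterns.

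| Pattern | At most two symptoms | Sum at most 2 | Highest grade at most 2 |
|---|---|---|---|
| 1 | yes | yes | yes |
| 2 | yes | yes | yes |
| 3 | yes | no | no |
| 1+1 | yes | yes | yes |
| 1+2 | yes | no | yes |
| 1+3 | yes | no | no |
| 2+2 | yes | no | yes |
| 2+3 | yes | no | no |
| 3+3 | yes | no | no |
| Total met | 9 | 3 | 5 |

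Count and points differ on 9 − 3 = 6 patterns. A sum of at most 2 implies at most two symptoms, because each present symptom scores at least 1. The points reading therefore never dates resolution earlier than the count. The third reading is weak: a patient with many moderate symptoms would meet the symptom part of resolution.

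**What happens at entry?** Assume that *systemic* means the flu-like domain, where entry needs at least 4 points. On Day 1 no entrant meets a sum of at most 2. Four two-symptom patterns (1+3, 2+2, 2+3, 3+3) already meet the count. Nobody is resolved at entry under any reading, since entry needs at least 37.8 °C and resolution at most 37.3 °C.

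**Can these patterns be turned into a size?** List length is not given, so it has to be assumed. For four items there are 28 unordered eligible patterns; the count is met by 4 (4/28 = 14.3%) and the highest-grade reading by 9 (9/28 = 32.1%). For eight items the numbers are 4 and 39 of 158 (2.5% and 24.7%). Counting ordered patterns for four items, 256 − (1 + 4 + 10 + 20) = 221 are eligible, and the figures become 36/221 = 16.3% and 50/221 = 22.6%. The fractions move with the list length and the counting convention. None is weighted by how often patients show the pattern.

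**Is the domain open?** Footnote 3 and inclusion criterion 2 both divide the symptoms other than temperature into a general flu-like group and a local nasal, throat and chest group. *Systemic* fits the first. The item list is missing from the summary, but the domain can be inferred.

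**Do the extra temperatures matter?** The endpoint is diary-based and the scheduled diary readings are morning and evening. The stated indications for an antipyretic are above 38.5 °C, or above 38.0 °C with certain comorbidities. A reading before an indicated dose is therefore well above 37.3 °C. It can alter the date only where the scheduled readings alone would show no fever. The summary also allows for doses given without an indication, and there the reading could be anything. The frequency is not given.

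**Does the per protocol set turn on the unit?** Footnote 6 already supplies the principle: if "the fact of reaching the primary endpoint by the patient can still be determined, the patient will be eligible for PP analysis". Take one mild symptom, one missing score and the rest absent. The count is then 1 to 2 (met), and the sum is 1 to 4 (undetermined). That leaves one diary entry open, not necessarily the date of recovery.

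**Is the sample size touched?** With a difference of 1 day, SD 2.5 days, two-sided 5% and 80% power, the plan's formula gives (1.960 + 0.842)² × 2 × 2.5² / 1² = 98.1, so 99 per arm and 198 in all, against the stated 200. Then 200 / (1 − 0.5) = 400, as stated. Power at 100 per arm is 80.7%. The SD comes from another study, and the documents do not say whether it used the same resolution rule. If the SD were 2.0 or 3.0 days (an assumed range), power would be 94.2% or 65.4%. Nothing ties either value to one reading of the rule.

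**The case for a change.** The strongest case is that careful readers could disagree: the wording suits a count, while the entry criterion suits points. Setting aside the weak highest-grade reading still leaves six of nine patterns in dispute. Under the count, some entrants would already meet the symptom part on Day 1, so temperature alone would date their recovery unless symptoms worsened. Under points, none would. Stating the unit would cost a few lines and need no new data.

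This stands as a remark on incomplete wording. It does not show a wrong rule. It names no better unit, and it would be fully met by copying in text that the full protocol or diary instructions may already hold.

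The type I error argument is weaker than it looks. With three equally correlated two-sided tests, the chance that any is significant in either direction is 7.3% at a correlation of 0.95 and 12.5% at 0.50, with a ceiling of 3 × 5% = 15%. That includes results favouring placebo. Picking the reading most favourable to the drug gives false superiority of 3.7% to 6.3% at the same correlations, against 2.5%, with a ceiling of 3 × 2.5% = 7.5%. All these figures use assumed correlations, count the weak third reading as an equal, and suppose a choice made after unblinding. Nothing in the documents suggests such a choice.

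**Conclusion.** No change to the plan follows. The summary leaves out the unit, the item list and the status of the readings before an antipyretic. These are details that analysts fill from the sponsor's intention and the diary instructions. The same rule applies to both arms of a double-blind trial, so the missing words do not by themselves favour either arm.

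The size cannot be stated beyond the pattern counts: count and points differ on 6 of 9 one- or two-symptom patterns, and the share of patients affected and the effect on the difference between arms are not derivable. The planned 200 per-protocol patients reproduce as 198 and are not in dispute.

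The conclusion assumes that the sponsor has one intended unit, recorded or at least settled before unblinding, and that *systemic* refers to the general flu-like domain. If the unit proved to have been chosen with treatment codes known, that would be a different and more serious matter, but the documents give no sign of it.

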14. Medical history of mental diseases of the patient or their parent(s)/adoptive parents.
15. Participation in other clinical trials for 3 months prior to enrollment in this study.
16. Patient's parents/adopters who are related to any of the on-site research personnel directly involved in the study or are an immediate relative of the investigator. 'Immediate relative' means husband, wife, parent, son, daughter, brother, or sister (regardless of whether they are natural or adopted).
17. The patient's parent/adopter who works for OOO "NPF "MATERIA MEDICA HOLDING" (i.e. the company's employees, temporary contract workers, designated officials responsible for carrying out the research or any immediate relatives of the aforementioned).

Criteria for Withdrawal or Termination

1. Screening failure.

2. Failure or refusal of the patient to follow the protocol.
3. The necessity to use medications not permitted in the study.
4. An adverse event requiring discontinuation of the study drug.
5. Patient's or his/her parent's/adopter's decision to withdraw early for lack of efficacy or other reasons.
6. Pregnancy.
7. Cases not stipulated in the protocol where the investigator decides that further participation may harm the patient.
8. Eligibility error.

Number of patients

It is planned to include 400 patients, 360 of them will be randomized which is expected to yield at least 200 patients (100 per Raphamin and Placebo groups) completing all the protocol procedures.

Interim analysis

The protocol does not schedule unblinded interim analyses. At the sponsor's decision, blinded interim analysis may be carried out to specify population parameters and potential further specification of sample size (increase only).

Treatment

Group I

Name of the medicinal product: Raphamin

Active ingredient: affinity purified antibodies to human interferon-gamma – 10 000 UMA*,
affinity purified antibodies to CD4 – 10 000 UMA,
affinity purified antibodies to β 2-microglobulin major histocompatibility complex class I – 10 000 UMA,
affinity purified antibodies to β 1-domain of major histocompatibility complex class II – 10 000 UMA

* UMA – Units of Modifying Activity.

Excipients: lactose monohydrate, microcrystalline cellulose, magnesium stearate.

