Schedule of study procedures

Procedure/Visit	Visit 1 (Day 1)	Visit 2 (Day 5±1)	Visit 3 (Day 7±1)	Visit 4 (Day 14±1)
Informed consent	+			
Registration of a study patient in the IVRS* and assignment of patient ID	+			
Complaints collection	+	+	+	
Medical history	+			
Concomitant diseases and conditions	+	+	+	+
Physical examination	+	+	+	
ARVI symptoms	+	+	+	
Concomitant therapy	+	+	+	+
SARS-CoV-2 rapid test	+			
Pregnancy test	+			
Inclusion/exclusion criteria	+			
Randomization	+			
Nasopharyngeal swabs for PCR	+			
Safety laboratory tests**	+		+	

Procedure/Visit	Visit 1 (Day 1)	Visit 2 (Day 5±1)	Visit 3 (Day 7±1)	Visit 4 (Day 14±1)
Study drug supply	+			
Antipyretic drug supply	+			
Evaluation of the study drug safety	+	+	+	+
Patient diary	+	+	+	+
Study drug accountability and return			+	
Treatment compliance			+	
Visit completion	+	+	+	+
Telephone survey				+
Study completion***				+

* Interactive voice/web response randomization system
 ** Laboratory tests include hematology, urinalysis, serum chemistry (total protein, C-reactive protein, glucose, total bilirubin, creatinine, ALT, AST, cholesterol). Performed with availability of signed PIS and ICF including the patient's consent for blood and urine sampling.
 *** In case of early withdrawal the procedure may be carried out at Visits 1, 2 or 3.

Statistical Analyses

SAS-[9.4].⁵ will be used for data processing and statistical calculations.

Samples

Total set: all enrolled patients who have signed ICF. This sample will consider all the recorded AEs, including those occurred prior to the study therapy.

Safety population: all included and randomized patients who received at least one dose of the study drug. This sample will be used for **analysis of the study treatment safety and tolerability**, as all adverse events identified after the study drug administration will be recorded.

Full Analysis Set. This sample includes all enrolled patients, except for those who met at least one of the following events:

- 1) non-compliance with inclusion / exclusion criteria;
- 2) patient did not take a single dose of the study drug;
- 3) lack of any data about the patient after administration of the study drug.

This sample, the most consistent with the “Intention-to-treat” principle, will be used for the **Intention-to-treat analysis (ITT analysis)** of the study therapy efficacy.

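### Post-dose safety laboratory tests and the tablet count are scheduled only at Visit 3, so a dosed patient closed out earlier may have no value for safety endpoint 3

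*Combined protocol and SAP*

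**What the plan says.** All references are to the combined protocol and SAP.

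- **Endpoint.** Safety assessment, item 3: "Percentage of patients with clinically relevant laboratory abnormalities". No denominator is given.
- **Laboratory timing.** In the schedule of study procedures, the row "Safety laboratory tests" is marked at Visits 1 and 3 only. The Study design text agrees: "At Visit 3 laboratory tests will be performed and compliance will be checked". The Visit 1 sample belongs to the work-up after consent and before randomisation.
- **Visit 2 (Day 5±1).** The text lists: "At Visits 2 and 3, the investigator will perform an physical examination, document changes in the symptoms and concomitant medications, and check patient diaries". No laboratory test is among these. Visit 4 is a telephone call.
- **Drug return and compliance.** Both rows are marked at Visit 3 only.
- **Early withdrawal.** Footnote ***, on the study completion row: "In case of early withdrawal the procedure may be carried out at Visits 1, 2 or 3". The schedule has no early-termination column.
- **Withdrawal criteria, item 4.** "An adverse event requiring discontinuation of the study drug".
- **Safety population.** "all included and randomized patients who received at least one dose of the study drug".
- **Analysis.** The Safety parameters section describes adverse event tables only. Data presentation promises frequency tables by visit for categorical variables. Neither says what to do when the post-dose laboratory value is missing.

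**The concern.** Whether a patient has a post-dose laboratory value depends on reaching Visit 3, and an adverse event is one of the listed reasons for not reaching it. The missing values can therefore be related to tolerability.

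The analysis text does not settle how such patients enter the percentage. If every dosed patient is in the denominator, an unsampled patient is in effect counted as normal. If unsampled patients are left out, the percentage describes only those who stayed to Visit 3. Either figure can understate the abnormality rate, and a reader of the results could not tell which had been used or how many values were missing in each arm.

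The tablet count has the same gap. The listed diary contents are temperature, symptoms, antipyretic use and any worsening. Study drug intake is not among them, so the diary as described does not replace the count.

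**Working it through.** **1. The plan's own figures.** Inputs from Evaluation of sample size: difference 1 day (worded as an upper bound), SD 2.5 days, two-sided α 0.05, power 80%, allocation 1:1.

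- Per arm: n = 2 × (1.960 + 0.842)² × 2.5² / 1² = 98.1, rounded up to 99. The total is 198, against 200 stated.
- Consented: 200 / (1 − 0.5) = 400.
- Footnote 9: 400 × (1 − 0.10) = 360 randomised; 360 × (1 − 0.444) = 200.2; composite loss 1 − 0.9 × 0.556 = 0.4996.

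The figures reproduce. The 10%, which covers screening failures and other discontinuations together, is fully used between 400 and 360. The 44.4% is lack of PCR confirmation, not departure from the trial. No separate rate of withdrawal after dosing can be taken from the plan.

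**2. One patient followed through the schedule.** Take a child who is dosed on Day 1, stops for an adverse event on Day 3 and is closed out at Visit 2.

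| Item | Scheduled for this child? |
|---|---|
| Laboratory panel at Visit 1 | Yes, before dosing |
| Laboratory panel at Visit 2 | No |
| Laboratory panel at Visit 3 | Not reached |
| Drug return and compliance (Visit 3) | Not reached |
| Member of the safety population | Yes |

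**3. Timing of the Visit 3 sample.** Treatment lasts 5 days and Visit 3 spans Days 6 to 8, so the sample falls 6 − 5 = 1 to 8 − 5 = 3 days after the last treatment day. What early leavers lack is a post-dose sample; completers have no scheduled sample during treatment either.

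**4. Number of patients (assumed rates).** Patients without a post-dose sample = 360 × w, where w is the share closed out before Visit 3.

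| w (assumed) | Patients of 360 | Per arm if equal |
|---|---|---|
| 1% | 3.6 (about 4) | 1.8 |
| 2% | 7.2 (about 7) | 3.6 |
| 5% | 18 | 9 |
| 10% | 36 | 18 |

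**5. Effect on the percentage (illustration only).** Every rate here is assumed, and all 360 are taken as dosed. Let the abnormality rate be 2% in sampled patients and 25% in unsampled ones, with w = 5%.

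- True rate: (0.02 × 342 + 0.25 × 18) / 360 = 11.34 / 360 = 3.15%.
- Sampled patients only: 2.0%.
- All dosed patients as denominator: 0.02 × 342 / 360 = 1.9%.

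With w = 1% the three figures are 2.23%, 2.0% and 1.98%. If unsampled patients had the same 2% rate as the others, the sampled-only figure would be unbiased and the all-dosed figure slightly low. The direction and size of any bias therefore rest on a difference that the documents do not establish.

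**The case against.** The best defence is that the document calls itself a protocol summary. It refers to a compliance formula that it does not print, so an early-termination procedure may exist in a fuller text. The footnote is also permissive: it does not forbid a sample at close-out, and a patient who stops drug may still attend Visit 3. Safety evaluation is scheduled at every visit and Visit 2 includes a physical examination. No hypothesis test is tied to safety endpoint 3, and the schedule is the same in both arms. All of this stands and limits the weight of the point. It does not remove it: nothing supplied requires the sample, and sites left to choose may act differently.

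A reader might infer several stronger things that the documents do not support:

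- **That only early leavers lack an on-drug value.** Visit 3 follows the 5-day course in completers too.
- **That Visit 1 close-out is an equal route.** Screening failure is itself a withdrawal criterion, so that provision mainly serves undosed patients. A dosed patient fits only if withdrawn on Day 1.
- **That the missing patients are those most likely to be abnormal.** An adverse event that stops treatment need not be a laboratory event.
- **That the unsampled group is as large as the expected number of abnormalities.** Both percentages would have to be assumed, so the comparison only reflects the values chosen.
- **That exposure is wholly unknown, or that abnormalities would pass unseen.** What is missing is a scheduled tablet count and a scheduled sample; clinical safety assessment continues. For efficacy, inability to assess compliance is already a listed deviation that may exclude data from the per protocol set.

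**Conclusion.** The point holds as a gap in data collection for a named safety endpoint. Followed as written, the schedule allows a dosed patient who leaves before Visit 3 to remain in the safety population without a post-dose laboratory value or a tablet count, and the analysis text has no rule for that patient.

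The size cannot be derived from the plan. About 4 to 36 patients would be affected under an assumed 1% to 10% early close-out. The low end is more credible, since the plan's sample size arithmetic leaves no further loss of this kind after randomisation. The conclusion assumes that no early-termination procedure exists outside the documents supplied. It is a cheap improvement worth making, and it leaves the primary endpoint and the sample size unchanged.

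**What to change.** 1. Amend footnote *** so that any patient who took at least one dose and is closed out before Visit 3 has the planned Visit 3 laboratory panel and the drug return and count at the close-out visit, subject to the consent to blood and urine sampling required by footnote **. If a fuller protocol already says this, carry it into the schedule.
2. State in the statistical section that safety endpoint 3 is reported among dosed patients with a post-dose sample, and show by arm the number of dosed patients without one.

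Whether to count only abnormalities that are new or worse than at Visit 1 is a separate decision on the endpoint's definition and is not needed to close this gap.

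The cost is one footnote and one sentence of analysis text. The panel is already planned and would be drawn earlier in a few patients. Some who withdraw will decline it, so the gap will shrink but not close, which is why the count of unsampled patients should be reported.
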